- The center will attempt to contact the subject and reschedule the missed visit and counsel the subject on the importance of maintaining the assigned visit schedule and ascertain if the subject wishes to and/or should continue in the study
- A minimum of 3 attempts (i.e., 2 phone calls followed by a certified letter, or other traceable letter, if necessary) should be made to contact the patient or patient's next of kin for each missed follow-up visit and this information should be documented in the subject's medical record or study file.
- Should the subject continue to be unreachable through the 12-month visit, he or she will be considered to have withdrawn from the study with a primary reason of lost to follow-up.

9.4. Subject Status and Classification

Table 9-1 describes subject status/classification and associated forms.

Table 9-1: Subject Status and Classification

Classification	Description
Screen Failure	A subject who signs an ICF but does not meet clinical eligibility criteria and/or is not treated or attempted to be treated with a WATCHMAN FLX Pro device is considered a screen failure. Screen failure subjects do not count towards the enrollment ceiling and will not be used for the primary analyses. Screen failure subjects should exit from the study immediately upon determining ineligibility. The original signed ICF must be maintained in the center's subject file.
Attempt	A subject who signs an ICF, meets eligibility criteria, and has had a WATCHMAN Access Sheath inserted to implant the device, but does not receive a WATCHMAN FLX Pro device will be classified as "Attempt." Subjects in which a WATCHMAN FLX Pro device is inserted into a different anatomical location/structure (not within the LAA) will also be classified as "Attempt." Attempt subjects will be followed for 12 months from the time of the implant attempt and adverse events will be collected. Attempt subjects will not undergo protocol required imaging at 45 days or 12 months. Attempt subjects are considered enrolled and therefore count towards the enrollment ceiling. Attempt subjects will be used for analyses of the ITT analyzed endpoints. The original signed ICF must be maintained in the center's study file and the following forms must be completed. 
 • eCRFs in the Baseline and Implant folders • Follow-up Visit Form(s), except LAA imaging • Adverse Event forms and/or Device Deficiency forms for any reportable adverse event that occurs after signing the ICF • End of Study form for withdrawal The date of withdrawal should be indicated in the End of Study form as the point of subject withdrawal.
Implant	A subject who signs an ICF, meets eligibility criteria, and is implanted with the WATCHMAN FLX Pro device will be classified as "Implant." Implanted subjects are those where the device has been deployed and implanted in the correct anatomical position (LAA). These enrolled subjects are followed in accordance with the follow-up schedule and data will be included in all study analyses. All applicable case report forms per the protocol must be completed. The original signed ICF and any relevant documentation must be maintained in the center's study file.

Abbreviations: eCRF=electronic case report form; ICF=Informed Consent Form; LAA=left atrial appendage

9.5. End-of-Study Definition

This clinical study will be considered completed when subjects are no longer being examined or the last subject's last study visit as outlined in the data collection schedule (**Table 10-1** below) has occurred. All enrolled subjects will be evaluated clinically peri-procedural through discharge, and at 45 days, 6 months, and 12 months post index procedure (preferably all in-person visits).

At the point of study completion and/or withdrawal, all open adverse events must be assessed by the investigator. These events must be closed or documented as ongoing. Events assessed as related to the device should be followed through resolution if possible and if consent has been provided by the subject for data collection on these events.

10. Study Methods

10.1. Data Collection

This section lists the data needed to fulfill the objectives of this clinical study.

The data collection schedule is provided in **Table 10-1**. Additional information, including recommended post-procedure medical therapy, is provided in Section **10.2** through Section **10.12**.

Table 10-1: Data Collection Schedule

Procedure/Assessment	Baseline Assessment ^h	Index Procedure (WATCHMAN FLX Pro)	Follow-up Visits		
			45-Days (±15 days) Follow-up & Imaging (Office)	6-Months (±30 days) Follow-up (Office or Telephone)	12-Months (±30 days) Follow-up & Imaging (Office)
Informed consent process (including informed consent signature date)	X	--	--	--	--
Demographics	X	--	--	--	--
Physical assessment	X	--	--	--	--
HAS-BLED & CHAD ₂ DS ₂ -VASC scores	X	--	--	--	--
Medical history	X	--	--	--	--
Pre-procedure LAA imaging (TEE/CT) ^c	O	--	--	--	--
Pregnancy Test ^d	X	--	--	--	--
Procedure and device information, procedure & discharge assessments	--	X	--	--	--
Procedural Imaging (TEE/ICE) ^b	--	X	--	--	--
Follow-up LAA imaging (TEE) ^b	--	--	X ^a	O	X ^a
Modified Rankin Scale ^e	X	X ^g	X ^g	X ^g	X ^g
Medication Regimen Review (anti-coagulation, anti-platelet, aspirin)	X	X	X	X	X
Adverse event assessment and device deficiency monitoring ^f	--	X	X	X	X

X = required; O = optional but recommended; -- = not required

^aImplant subjects only (does not include Attempts). TEE imaging for core lab analysis is required at the 45-day and 12-month visits and must be submitted to the sponsor.

^bAll TEE, CT, and ICE images collected as part of the procedure and follow up visits (protocol defined, unscheduled, or SOC) through 12 months should be submitted for core lab analysis. Imaging collected as part of pre-procedure planning will not be submitted to the core lab. Collection of these images at the 6-month and unscheduled visits is not a protocol requirement. It is recommended that imaging be performed after a neurological event to screen for Device Related Thrombus. Image collection during the index procedure and at the 45 day and 12-month imaging visits must be collected by study personnel trained to the Imaging Manual.

^cPre-procedural planning imaging (TEE / CT) is recommended per the IFU if ICE will be used to guide the implant procedure.

^dRequired prior to implant for subjects of childbearing potential, who are pregnant or plans to become pregnant during the time of the study (method of assessment per investigator discretion.)

^emRS assessments should be performed by trained and certified study personnel (or Neurologist).

^fSafety events will be monitored and reported to Boston Scientific Corporation per **Section 17.1**. Please refer to **Section 19.2** for a list of events to be adjudicated by the CEC through completion of a subject's participation in the study and **Table 17-1** for definitions of these events, which specify data required for CEC adjudication. Reporting of device deficiencies will follow applicable regional post-market safety surveillance requirements.

^gmRS is to be conducted ONLY if there is a neurological event. Collection is required at the time of the event and 90d post-event per **Section 10.9**.

^hSome baseline assessments including Informed Consent may be collected after treatment with a WATCHMAN FLX Pro device per **Section 10.3 & 10.4**.

10.2. Study Candidate Screening

Investigators are responsible for screening all subjects and selecting those who are appropriate for study inclusion as per the product IFU. No study-specified procedures or tests will be done prior to consent, though studies, tests, or procedures performed as part of the normal standard of care may be performed prior to consent.

10.2.1. Strategies for Recruitment and Retention

Subjects may be recruited through the Investigator's practice, referring physicians, and/or the use of recruitment tools. Potential subjects may be identified through an investigational center's database query (chart reviews) or as new or existing patients attend clinic visits. Any information disseminated to potential patients (e.g., advertisements, pamphlets, posters) must be approved by the investigational center's IRB prior to use.

Investigators should make efforts to screen and enroll diverse and previously underrepresented patient populations in LAAC trials, including women and minorities. Boston Scientific seeks to enroll diverse populations including representative proportions of relevant age, racial, and ethnic subgroups, which are consistent with the intended use population of the devices. Therefore, case report forms will collect data on age, race, and ethnicity. To ensure a diverse population is enrolled, BSC reserves the right to restrict enrollment to patients of diverse and previously underrepresented populations. Should enrollment restrictions be placed on sites, restrictions will be communicated via the Enrollment Guide(s).

Note: With a goal of achieving an unbiased estimate of treatment effect in the general population, Boston Scientific seeks to enroll a diverse population including representative proportions of relevant age, racial, and ethnic subgroups, which are consistent with the intended use population of the device. Case Report Forms will collect data on age, race and ethnicity in order to achieve this goal (<https://www.fda.gov/media/98686/download>)

Follow-up visits should be performed per local practice and every effort must be made by the site to retain study patients for the duration of the study and to collect patient data per the Data Collection Schedule in Section 10.1.

10.3. Informed Consent

Subjects must sign the approved study ICF before any non-standard of care, study specific assessment can be assessed. If all baseline and procedure assessment/procedures are SOC, a subject may sign the ICF after receiving the WATCHMAN FLX Pro device. Subjects that have signed and dated the ICF, have met all clinical inclusion and no clinical exclusion criteria, and have been treated with or attempted to be treated with a WATCHMAN FLX Pro device are considered enrolled in the study. The original, signed document is to be kept with the subject's file and a copy must be provided to the subject. The informed consent process must be documented by the person obtaining consent and the documentation must be placed in the subject's file.

The Investigator/designee who has been trained on the protocol will explain the nature and scope of the study, the potential risks and benefits of participation, and will answer questions for the subject. Patients must be given ample time to review the ICF and have questions answered before signing.

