---------------------------	---

Abbreviation: IC=inclusion criterion

8.3. *Exclusion Criteria*

Subjects who meet any one of the following criteria (see **Table 8-2**) will be excluded from this clinical study. No vulnerable populations will be enrolled in this study.

Table 8-2: Exclusion Criteria

Exclusion Criteria	
EC1. Subject has a documented life expectancy of less than 6 months.
 
EC2. Subject is currently enrolled in another investigational study, except if the subject is participating in a mandatory governmental registry, or a purely observational registry with no associated treatment.
 
EC3. Intracardiac thrombus is present.
 
EC4. An atrial septal defect repair or closure device or a patent foramen ovale repair or closure device is present.
 
EC5. The LAA anatomy will not accommodate a Closure Device.
 
EC6. The patient has known hypersensitivity to any portion of the device material or the individual components such that the use of the WATCHMAN FLX™ Pro Device is contraindicated.
 
EC7. Any of the customary contraindications for other percutaneous catheterization procedure (e.g., patient size too small to accommodate TEE probe or required catheters) or conditions (e.g., active infection, bleeding disorder) are present.
 
EC8. There are contraindications to the use of anticoagulation therapy, aspirin, or P2Y₁₂ inhibitor.
 
EC9. Subject is of childbearing potential and is, or plans to become, pregnant during the time of the study (method of assessment per study physician's discretion).

---------------------------	--

Abbreviations: EC=Exclusion Criteria; LAA=left atrial appendage; TEE=transesophageal echocardiography

9. Subject Accountability

9.1. *Point of Enrollment*

Subjects are considered enrolled in the study when the subject signs an ICF approved by the IRB, all clinical inclusion and no clinical exclusion criteria have been met, and the WATCHMAN FLX Pro device has been used for treatment and/or attempted to be used for treatment. Both Attempt and Implant subjects as defined in **Table 9-1** are considered enrolled subjects. A subject who is determined to not meet study specific clinical eligibility criteria after signing consent will be considered a screen failure (see **Table 9-1**) and will not count towards the enrollment ceiling.

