10.4. Baseline Assessments

The following pre-procedure data should be collected within 30 days prior to the index procedure for all patients but will follow local standard of care practice. If mRS is not standard of care prior to the Index Procedure, it is to be collected by study personnel per Section 10.9.1. Baseline assessments performed per Standard of Care outside of the 30-day window can be used and will not be a protocol deviation if no data within 30 days are available. Assessments indicated with an '*' are expected to be collected prior to implant.

- Confirmation of eligibility criteria
- Clinical assessments
 - Demographics, including age at time of consent, race, ethnicity, and sex
 - Medical, cardiac, and neurological history including cardiovascular diseases, AF type (paroxysmal/persistent/permanent) and time since AF diagnosis; prior history of ischemic stroke, hemorrhagic stroke and/or TIA; previous cardiac procedures; history of bleeding and location; and NSAID use
 - HAS-BLED, and CHA₂DS₂-VASc scores*
 - Physical assessment includes height and weight*
 - Current medication regimen review for the use of antiplatelet, aspirin, and anticoagulant medications
 - Modified Rankin Scale (mRS)*
 - Pregnancy test for Women Of Childbearing Potential, who are pregnant or plans to become pregnant during the time of the study (method of assessment per investigator discretion) *
- Imaging assessments
 - Pre-procedural imaging (TEE / CT) is recommended per the IFU if ICE will be used to guide the implant procedure. *

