10.6. Index Procedure

The preparation of the subject for the transcatheter procedure will be performed following standard techniques. Refer to the WATCHMAN FLX Pro LAA Closure Device IFU and the WATCHMAN® Access System IFU for detailed instructions regarding device use.

NOTE: If using a new to the market WATCHMAN Access System, it is recommended that the implanting physicians do not utilize the new access system until they have successfully implanted at least five (5) WATCHMAN FLX Pro devices with their standard access system.

The procedure should be performed using standard of care methods established by the investigational site (e.g., sterile technique, personnel requirements, etc.). Implantation of the WATCHMAN FLX Pro Device shall only be performed by study physicians trained in percutaneous and transseptal procedures who have completed the WATCHMAN FLX Pro physician training program. Refer to the applicable WATCHMAN FLX Pro Instructions for Use (IFU) for detailed instructions regarding the implantation and use of the WATCHMAN FLX Pro Device.

The following information will be collected in the eCRF during the procedure. The study eCRFs identify the specific data points to be collected.

- Current medication regimen review for the use of antiplatelet, aspirin and anticoagulant medications.
- Adverse events experienced at implant procedure. Refer to Section **17** for detailed information on Safety reporting.
- Procedure related data including:
 - WATCHMAN FLX Pro Device usage information, including device size and compression post-implant
 - Access System(s) usage information
 - Transseptal Access System usage information
 - LAA imaging information (TEE/ICE): LAA size/shape, number of lobes in LAA, and location of lobes to ostium
 - Device release criteria measurements
 - Name of implanting physician
 - Duration of procedure and fluoroscopy
 - Procedural medications
 - Type of anesthesia
 - Device Deficiencies
- TEE / ICE images must be submitted for core lab analysis for independent analysis. Image collection during the index procedure must be collected by study personnel trained to the Imaging Manual.

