10.9.1. Stroke Scales and Cognitive Assessment

The Modified Rankin Scale (mRS) score assesses the severity of stroke disability and functional dependence of all subjects. The assessment should be performed by either a neurologist or personnel who have completed a certification for the mRS. The mRS must be collected for all subjects at Baseline. If mRS is not standard of care prior to the Index Procedure, it is to be collected by study personnel. Additionally, mRS must be collected following any stroke or TIA event and at 90 (\pm 15) days after a stroke or TIA event. The mRS collected following the stroke or TIA event, and at 90 (\pm 15) days after a stroke or TIA event, may be obtained by non-study personnel.

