	Provide all relevant source documentation (de-identified/ pseudonymized) for reported event.	
 Upon request of sponsor

17.5. *Device Deficiencies*

Device deficiencies will be documented and reported to BSC. If possible, the device(s) under study should be returned to BSC for analysis following the commercial complaints process. Device deficiencies should also be documented in the patient's source records.

Device deficiencies should not be reported as AEs. Instead, they should be reported on the Device Deficiency eCRF. If an ADE/SADE results from a device deficiency, the ADE/SADE should be reported on the appropriate eCRF through study end.

17.6. *Reporting to Regulatory Authorities / IRBs / Investigators*

BSC is responsible for reporting adverse event information to all participating Principal Investigators, IRBs, and regulatory authorities, as applicable.

The Principal Investigator is responsible for informing the IRB and regulatory authorities of UADEs and SAEs as required by local/regional regulations.

18. Informed Consent

Subject participation in this clinical study is voluntary. Informed Consent is required from each subject. The investigator is responsible for ensuring that Informed Consent is obtained prior to the use of any non-standard of care, study specific assessment and/or testing. If all baseline and Index Procedure assessments/procedures are SOC, a subject may sign the ICF after receiving the WATCHMAN FLX Pro device.

The obtaining and documentation of Informed Consent must be in accordance with the principles of the Declaration of Helsinki, ISO 14155, any applicable national regulations, and local Ethics Committee and/or Regulatory authority, as applicable. The ICF must be accepted by BSC or its delegate (e.g., CRO), and approved by the site's IRB, or central IRB, if applicable.

Boston Scientific will provide a study-specific template of the ICF to investigators participating in this study. The ICF template may be modified to meet the requirements of the investigative site's IRB. Any modification requires acceptance from BSC prior to use of the form. The ICF must be in a language understandable to the subject and if needed, BSC will assist the site in obtaining a written consent translation. Translated consent forms must also have IRB approval prior to their use. Privacy language shall be included in the body of the form or as a separate form as applicable.

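### Consent may follow the implant: event-recording wording should be aligned for late signers, and a descriptive table by consent timing is worth considering, mainly for the Access System test

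*Protocol*

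**What the plan says.** **Late signature is allowed.** Protocol 10.3 says "If all baseline and procedure assessment/procedures are SOC, a subject may sign the ICF after receiving the WATCHMAN FLX Pro device", and Protocol 18 repeats it: "If all baseline and Index Procedure assessments/procedures are SOC, a subject may sign the ICF after receiving the WATCHMAN FLX Pro device". The synopsis, Protocol 7.1 and a footnote to Table 10-1 agree. The only time limit is implicit: "Subjects must sign the approved study ICF before any non-standard of care, study specific assessment can be assessed".

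**The route is conditional.** On the modified Rankin scale, Protocol 10.9.1 says "The mRS must be collected for all subjects at Baseline", and Protocol 10.4 adds "If mRS is not standard of care prior to the Index Procedure, it is to be collected by study personnel". For imaging, Protocol 10.6 says "Image collection during the index procedure must be collected by study personnel trained to the Imaging Manual". A site where any of this is not standard of care must obtain consent first.

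**A signature defines the sets.** Protocol 9.1 says "Subjects are considered enrolled in the study when the subject signs an ICF approved by the IRB", with eligibility and treatment or attempted treatment as further conditions. The ITT set (Protocol 11.2.1, SAP 4.2), the first 500 subjects and the first 300 TruSteer subjects are all drawn from enrolled subjects. The screen-failure class also needs a signature, so a treated patient who never signs appears nowhere.

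**Event recording is described in two ways.** Protocol 11.1.2.3 and the opening of 17.1 start at the index procedure. The Attempt row of Table 9-1 asks for reportable events arising once the ICF is signed. A later paragraph of 17.1 limits recording to events after consent and enrollment, and then adds that events before, during or after the procedure are included.

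**The concern.** Implant success is fixed at the procedure, and the safety composite counts death, stroke, systemic embolism and major bleeding from the index procedure. If patients approached afterwards sign less often when the implant failed or an early event occurred, both observed rates look better than the true ones. The z-tests against 94% and 21% make no allowance for this.

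No planned analysis would show it. The tipping-point analysis in Protocol 11.1.2.3 concerns enrolled subjects with inadequate follow-up. The subgroups in SAP 5.3 do not include consent timing. The regressions in SAP 5.4 cover effectiveness and safety but not implant success.

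A second problem needs no assumption about selection. For a subject who signs late and is enrolled, two passages read literally leave out procedural events before the signature, and those events belong in the safety composite.

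**Working it through.** **1. Event recording, passages side by side**

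| Place | Recording or counting starts at |
|---|---|
| Protocol 11.1.2.3 | index procedure |
| Protocol 17.1, opening | beginning of the index procedure |
| Protocol 17.1, later paragraph | after consent and enrollment, yet also events before or during the procedure |
| Table 9-1, Attempt row | after the ICF is signed |

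For someone who signs before the procedure these agree. For someone who signs afterwards they differ over the procedural period.

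**2. The plan's own figures.** Power = Φ{[|p1 − p0| − 1.96√(p0(1−p0)/n)] / √(p1(1−p1)/n)}.

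- Access System (SAP 3.3.2; 94% against 97.8%, n = 300): (0.038 − 1.96×0.01371)/0.00847 = 1.31, power 90.6%. The stated figure is above 90%, so it reproduces.
- Safety (Protocol 11.1.2.2; 21% against 14%, n = 485): (0.07 − 1.96×0.01849)/0.01576 = 2.14, power 98.4%. The stated figure is above 95%, so it is met.

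**3. Pass cutoffs.** The SAP does not state the variance form; the null variance is assumed.

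- Access System: 9 failures of 300 gives z = −2.19 and 10 gives −1.94, so the test passes at 9 or fewer. At the goal 18 failures are expected. Exact type I error is 1.3%.
- Safety: 84 events of 485 gives z = −1.99 and 85 gives −1.88, so the test passes at 84 or fewer. Exact type I error is 2.5%.

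**4. Access System under selective loss.** Let c be the share approached late and s the share of their failures lost, both assumed. The lost fraction is l = 0.06·c·s, and the observed failure rate is q = (0.06 − l)/(1 − l). For c = 0.50 and s = 0.5: l = 0.015, q = 0.045/0.985 = 4.57%. The false-pass chance is P(F ≤ 9 | 300, q).

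| | c = 10% | 25% | 50% |
|---|---|---|---|
| s = 0.25 | 1.7% | 2.4% | 4.2% |
| s = 0.5 | 2.1% | 4.2% | 11.8% |

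With the observed-rate variance the cutoff is 11. The chance is then 5.0% with no loss, and 7.3%, 12.7% and 28.0% for s = 0.5.

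**5. Safety under selective loss.** The only early-event figure in the documents is 0.5%, from the earlier single-arm study of the predecessor device (Protocol 4.1.2). Its composite differs: it ran to discharge or 7 days, counted ischemic stroke only, omitted major bleeding and included cardiac surgery. Suppose every such patient approached late is lost: x = 0.005·c, observed rate = (0.21 − x)/(1 − x). For c = 10%, 25% and 50% the observed rate is 20.96%, 20.90% and 20.80%, and type I error is 2.6%, 2.8% and 3.1%.

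**6. What a comparison by consent timing could detect.** At 94% success with half of the late failures lost, late signers show 0.03/0.97 = 3.1% failures against 6.0%, a gap of 2.9 points. The 95% half-width of the difference is 1.96√[0.06×0.94×(1/n_late + 1/n_early)]. With 30/270, 75/225 and 150/150 subjects this is 9.0, 6.2 and 5.4 points. The gap lies well inside every one of these.

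**7. Repeating the Access System test in early signers only.** With 10%, 25% or 50% late, n is 270, 225 or 150 and the cutoffs are 8, 6 and 3 failures. Exact power at 97.8% falls from 87% (n = 300) to 86%, 77% and 58%.

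**The case against.** Late consent is an openly stated choice in an observational study of a commercial device, and its reach is limited. All baseline and procedure assessments must be standard of care, including the Rankin score and index imaging by trained personnel. Attempts are explicitly enrolled and count in ITT. The Enrollment Guide and monitoring plan, which govern subset requirements and consent oversight, are outside the documents reviewed. The size of any bias is wholly assumed: three of the six Access System scenarios stay below 2.5%, and 11.8% needs half of patients approached late and half of their failures lost. All of this stands.

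The Access System test is also of uncertain status. Protocol 11.3.4 and SAP 4.2 confine the performance-goal tests to the Primary Analysis Subset, while SAP 3.3 specifies a test for the Access System subset. That must be reconciled, but it does not remove the point.

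A reader might infer three stronger things that the documents do not support:

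- **That failed attempts cannot sign late, so the route is one-sided by rule.** The clause speaks of receiving the device, but Protocol 10.2 says "procedures performed as part of the normal standard of care may be performed prior to consent", so failed attempts are not clearly barred. Crossovers to another access system do receive the device and count as TruSteer Attempts (SAP 4.1.4). A legal representative may also consent.
- **That the safety test is seriously exposed.** If 10% of six-month events were known before signing and 30% of those were lost, type I error would be 4.5%; with 50% known and 30% lost, 29%. Nothing in the documents gives those shares.
- **That a planned subset analysis would settle the matter.** Steps 6 and 7 show that it would not.

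The objection that endpoint counting is already settled by Protocol 11.1.2.3 is only partly right. That section says which events count, but an event that a site was told not to record cannot be counted.

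**Conclusion.** The point holds in limited form. Set membership can be settled after the procedural outcome is known, and no planned output shows how often that happens. Selection itself is not shown.

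If late consent were both common and selective, the exposure lies mainly in the Access System test: from 1.3% to between 1.7% and 11.8% on the assumed shares, with true success exactly at 94% and the null variance. On the 0.5% early-event assumption the effect on safety is negligible, at most 3.1% against 2.5%. That input comes from a different composite, so it is an illustration and not a bound. No claim is made about the 45-day leak endpoint.

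The event-recording conflict rests on the text alone and should be corrected. The table by consent timing is worth considering, not essential.

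**What to change.** 1. **Align event recording.** Amend the Attempt row of Table 9-1 and the later paragraph of Protocol 17.1 to match 11.1.2.3, so that events from the start of the index procedure are recorded for every enrolled subject whatever the ICF date. This is a wording edit only.

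2. **Add a descriptive table** under SAP 3.3.3 and 3.2.2. Give the number and share of subjects who signed before, on and after the procedure date, using the signature date already collected (Table 10-1). Same-day signatures form their own category, because a date does not show the order. Report implant success and the safety composite by category with confidence intervals.

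3. **State the table's limits in the SAP.** It has low ability to detect selection (about a 2.9-point gap against a half-width of 5 to 9 points for implant success). A null result is not reassurance. Missing the goal among early signers may only reflect the smaller number. Patients who never signed cannot be recovered.

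4. **Reconcile the status of the Access System test** between Protocol 11.3.4, SAP 4.2 and SAP 3.3.

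The cost is the wording edits, a few SAP sentences and one table. There are no new visits or data fields, and the primary sets and tests do not change.
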